Diagnosis and main criteria for inclusion:	
Male and female HLH patients of any age.
 
Patients diagnosed with confirmed or suspected pHLH defined by; a molecular diagnosis or familial history consistent with pHLH or fulfilment of at least five out of eight HLH-2004 diagnostic criteria
 
Presence of active disease
 
Presence of at least one of the following criteria, as assessed by the Investigator:
 
 • Unsatisfactory or no response to conventional therapy • Worsening on conventional therapy • Reactivation after initial response to conventional therapy • Intolerance to conventional therapy 
Expectation of survival beyond 1 week as judged by the investigator
 
Patient has expectation of proceeding to HSCT

Main criteria for exclusion:	
Diagnosis of secondary HLH consequent to a proven rheumatic, metabolic or neoplastic disease.
 
Active mycobacteria, Histoplasma capsulatum, Salmonella, or Leishmania infections.
 
Evidence of latent tuberculosis.
 
Presence of malignancy.
 
Existence of any severe co-morbidity or any other medical condition which, in the opinion of the investigator, makes the patient unsuitable for the treatment
 
Receipt of a Bacillus Calmette-Guérin (BCG) vaccine within 12 weeks prior to Screening.
 
Receipt of a live or attenuated live (other than BCG) vaccine within 4 weeks prior to Screening.
 
Pregnant or lactating female patients.

Assessments:	See schedule of events in Table 3 and Table 4
Test product; dose and mode of administration:	Emapalumab 5 mg/mL solution for intravenous infusion to be administered over a period of 1-2 hours in doses of 1, 3, 6 or 10 mg/ kg body weight twice weekly. Starting dose is 1mg/kg.
Reference product; dose and mode of administration:	Not applicable
Duration of treatment(s):	The duration of treatment is expected to last until HSCT.
Determination of sample size:	Sample size is not based on statistical considerations but the data from 10 up to 18 Chinese patients will add sufficient information to the safety and efficacy profile established during the global clinical development program for emapalumab in pHLH patients.
Statistical methods:	Safety and efficacy analyses will be conducted on the "All treated analysis set" which will comprise all patients who received at least one infusion of IMP.

2 Abbreviations and definition of terms

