6.1 Overall study design and plan

This is an open-label, single-arm, multi-centre study to collect safety and efficacy data on emapalumab in treatment experienced male and female patients diagnosed with pHLH. The study will be performed in China.

The study will recruit at least 10 patients, and up to 18 patients if enrolled within the recruitment period.

Patients should already have received conventional HLH therapy (treatment experienced patients), without obtaining a satisfactory response according to the investigator or having shown signs of intolerance to it.

Figure 1 summarizes the study design.

The study is divided into three parts: screening, treatment period, and follow-up. Patients will be admitted to the unit the day before the first administration of the study drug (study day minus one, SD-1).

Figure 1 Overview of the study design

SCREENING	TREATMENT					FOLLOW-UP					
Day -14 to Visit 1	Visit 1 (SD 0)	Visit 2 (SD 3-4 and onwards) every 3-4 days	W8 Primary assessment timepoint if treatment continues	W9-onwards until start of conditioning for HSCT	EOT (3±1 day after last infusion) Primary assessment timepoint if treatment stopped before week 8	Pre-HSCT		Post HSCT			
	Initial dose	Subsequent doses				Pre-conditioning	W 1/2/3	D 30	D 60	D 100	M6

Abbreviations SD, study day; EOT, end of treatment; HSCT, hematopoietic stem cell transplant; W, week; D, day after HSCT; M, month; EOS, end of study

The patient will enter screening after informed consent is obtained and will undergo screening assessments to confirm eligibility. Duration of the screening period will be kept as short as possible and should not exceed 2 weeks.

First emapalumab infusion, at a dose of 1 mg/kg, marks the start of the treatment period. The treatment period is foreseen to continue until start of conditioning for HSCT, if deemed indicated for this patient. Infusions will take place twice weekly, at a dose determined by the Investigator for each infusion, as described in Section 6.4.4. Emapalumab will be administered on the background of dexamethasone, which can be tapered or increased as needed. No wash-out is required prior to conditioning for HSCT.

Last visit of the treatment period is the end of treatment, which occurs 3 days after the last infusion of emapalumab. Assessment of efficacy objectives occurs at end of treatment.

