6.4.4 Selection and timing of doses for each patient

Initial dose of emapalumab (Gamifant®) is 1 mg/kg and it will be administered by intravenous infusion over a period of 1 hour. Depending on the volume to infuse and the individual patient's condition, duration of infusion can be extended to maximum of 2 hours. Infusions will be

performed twice per week (not more than 4 days apart, e.g. every Monday / Thursday, or every Tuesday / Friday).

Dose increase may occur any time during the study, if the clinical and laboratory criteria listed in the Table 5 are met. Dose increase will occur in a stepwise manner, from 1 mg/kg to 3 mg/kg, from 3 mg/kg to 6 mg/kg, and from 6 mg/kg to 10 mg/kg.

After the patient's clinical condition is stabilized, decrease the dose to the previous level to maintain clinical response.

The duration of treatment is expected to last until start of conditioning for HSCT (if HSCT deemed necessary) or unacceptable toxicity, but is not recommended to exceed 6 months.

No wash-out period is required between the last administration of emapalumab and the start of conditioning for HSCT.

Table 2 Clinical and Laboratory Criteria to Guide Dose Increase

Study Visit	Emapalumab Dose	Criteria for Dose Increase
Day 1	1 mg/kg	N/A

Study Visit	Emapalumab Dose	Criteria for Dose Increase

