6.5.6.2 Height and weight

Body weight (in kg) will be recorded at each visit during the treatment period, at the EOT visit, and at the final 1-year visit during the follow-up period (EOS)/discontinuation visit. Height (in cm) will be recorded at screening, at the EOT visit, and at the EOS/discontinuation visit. For patients older than 18 years of age height is only recorded at enrollment visit.

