#### **6.2.2. Derivation and Transformation on Data**

Besides the calculation for certain endpoints (as listed below), which are based on data collected via CRF, no derivation or transformation will be applied. Outliers will be reported to data management function as a data issue to be resolved or confirmed before database lock. No special data handling will be done.

For the derivation of the achievement of Overall Response, refer to [Section 6.8.2](#).

Age (in years) = (Date of informed consent/assent – birth date + 1)/365.25, rounding up to integer;

Time to first overall response (in days) = Date of the first achievement of response (Complete Response, Partial Response or HLH Improvement) – date of the first dose of emapalumab + 1, patients without a response will be censored at the date of EOT visit or last assessment;

Cumulative duration of response (in days) = Date of EOT visit – date of the first achievement of response + 1, for patients who achieve a response, lost that response, and then achieve any response subsequently, the total time in response will be calculated by adding together these separate periods in response;

Survival to start of HSCT conditioning (in days) = Date of death – date of first dose of emapalumab + 1, patients with no event will be censored at date of the start of conditioning for HSCT or last contact for patients who did not undergo HSCT;

Survival after HSCT (in days, calculated only for patients underwent HSCT) = Date of death – HSCT performed date+ 1, patients with no event will be censored at date of last contact;

Overall survival (in days) = Date of death – date of first dose of emapalumab + 1, patients with no event will be censored at date of last contact;

Dose administered (mg) = Prescribed dose [mg] × Approximate Proportion Administered [%];

Total duration of dosing (days) = Date of last infusion – date of first infusion + 1;

Average dosing frequency (times per day) = The total number of records of emapalumab infusion / total duration of dosing;

Prescribed dose change from first dosing (%) = (Prescribed dose at visit [mg] - prescribed dose at first dosing [mg]) / prescribed dose at first dosing [mg] × 100%.

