## **6.5. Exposure and Compliance**

IMP administration including level of dose prescribed, prescribed dose, date, time and duration of dose administration, and information on dose increase and dose interruption will be collected in the CRF.

The total prescribed dose, total dose administered, total duration of dosing (in days), and average dose frequency (times per day) will be summarized using descriptive statistics. The dose administered will be calculated based on prescribed dose and approximate proportion administered (refer to [Section 6.2.2](#)). The total duration of dosing will be calculated based on the date of last infusion and the date of first infusion (refer to [Section 6.2.2](#)). The average dosing frequency will be calculated based on the total duration of dosing and the total number of records of emapalumab infusion (refer to [Section 6.2.2](#)).

The emapalumab dose change from the first dosing will be summarized showing the number and percentage of patients with a dose increase or a dose decrease at each visit. Moreover, the percentage of dose increases and decreases from the first dose for each patient will be summarized using a descriptive table. Percentage of dose increase or decrease from first dose will be calculated based on prescribed dose at first dosing and prescribed dose at each visit (refer to [Section 6.2.2](#)).

Data listing containing all information collected for IMP administration will be provided. In addition, IMP administration will be listed at patient level including all dose adjustments over time and summarized in terms of the number of doses administered, maximum dose, equivalent dose of dexamethasone, duration of exposure from the first dose to the last dose of treatment, cumulative dose, average dose frequency and average dose per day.

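### The SAP measures emapalumab dose change against the first dose, which is the lowest level, so protocol step-downs never show as level decreases in the summary tables

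*SAP*

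**What the plan says.** **Derivation.** SAP 6.2.2 defines the variable as "Prescribed dose change from first dosing (%) = (Prescribed dose at visit [mg] - prescribed dose at first dosing [mg"]), divided by the prescribed mg at first dosing and multiplied by 100.

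**Tables.** SAP 6.5 keeps the first infusion as the reference and describes the by-visit output as follows: "summarized showing the number and percentage of patients with a dose increase or a dose decrease at each visit". It adds a descriptive table of the percentage change from first dose, which refers back to 6.2.2.

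**Listing and CRF.** SAP 6.5 also provides a patient-level listing of all dose adjustments over time. It states that the CRF collects the dose level prescribed as well as the prescribed dose.

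**Dosing.** The Protocol synopsis gives emapalumab "in doses of 1, 3, 6 or 10 mg/ kg body weight twice weekly. Starting dose is 1mg/kg". Protocol 6.1 repeats the starting point: "First emapalumab infusion, at a dose of 1 mg/kg, marks the start of the treatment period". Protocol 6.4.4 sets the upward path ("Dose increase will occur in a stepwise manner, from 1 mg/kg to 3 mg/kg", then to 6 and 10). For a patient whose condition has stabilized, it tells sites to "decrease the dose to the previous level to maintain clinical response".

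**Weight.** Protocol 6.5.6.2 states: "Body weight (in kg) will be recorded at each visit during the treatment period". I found no rule in either document on whether, or when, each mg dose is recalculated on current weight.

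**The concern.** The regimen moves in both directions between four mg/kg levels. The reference chosen for dose change is the floor of that range. No visit dosed at a protocol level can lie below the reference level, so a decrease category built on it has no room for the event the protocol instructs.

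A patient brought down from 6 to 3 mg/kg and a patient brought up from 1 to 3 mg/kg fall in the same cell of the by-visit table, and at constant weight both carry the same percentage. Someone reading only the tables could conclude that doses were raised and never lowered. In a study with flexible dosing, how far patients escalated and whether they could step down is useful context for the safety and response results. These two tables are the only summaries in the SAP text that name dose decreases.

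**Working it through.** **Inputs.** Levels 1, 3, 6 and 10 mg/kg, with the first dose at 1 mg/kg (Protocol synopsis, 6.1, 6.4.4). Formula from SAP 6.2.2. The documents give no figure of their own on this point to reproduce.

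**Formula.** With L the level at the visit, W the dosing weight at the visit and W0 the weight at first dosing:

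change (%) = (L × W − 1 × W0) / (1 × W0) × 100

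**Step 1: constant weight (W = W0).** This reduces to (L − 1) × 100, giving 0% at 1 mg/kg, +200% at 3, +500% at 6 and +900% at 10.

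**Step 2: the three one-level step-downs.** The change against the preceding level is (new − old) / old × 100. The last column applies the SAP formula if mg follows current weight and weight has moved by −20% to +20% since first dosing. That range is my assumption, for illustration.

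| Step (mg/kg) | Against preceding level | SAP formula, constant weight | Counted as (constant weight) | SAP formula, weight −20% to +20% |
|---|---|---|---|---|
| 10 to 6 | −40.0% | +500% | increase | +380% to +620% |
| 6 to 3 | −50.0% | +200% | increase | +140% to +260% |
| 3 to 1 | −66.7% | 0% | no change | −20% to +20% |

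**Step 3: when could a visit count as a decrease?** It requires L × W < W0, that is, a weight loss above 1 − 1/L. This is 66.7% at 3 mg/kg, 83.3% at 6 and 90% at 10. In practice only visits at 1 mg/kg can fall in the decrease category, and they get there through a smaller mg amount, not a lower level.

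**Step 4: patient held at 1 mg/kg.** If mg is recalculated on current weight, 10.0 to 9.6 kg gives (9.6 − 10.0) / 10.0 = −4%, a decrease, and a 5% gain gives +5%, an increase. The weights are illustrative. The SAP sets no tolerance around zero.

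**Step 5: would changing the unit be enough?** In mg/kg against the first dose, the possible values are 0%, +200%, +500% and +900%. No visit at a protocol level could then be a decrease, so the reference has to change as well as the unit.

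**Relevance.** Protocol 6.4.3 reports for study NI-0501-04 that 13 of 45 patients stayed at 1 mg/kg, 11 were raised to 3-4 mg/kg and 21 received 6 mg/kg or more. So 32 of 45 (71.1%) were escalated and could in principle have stepped down. The documents do not say how many did, so I give no expected count for this study.

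**The case against.** The strongest reply is that the table is right for what it claims. SAP 6.5 labels it as change from the first dosing, and a patient at 3 mg/kg after 6 is indeed above the first dose. The percentage summary helps too: at constant weight its four values map one-to-one to the four levels, so a shift of a few percent would not be mistaken for a level change. With 10 to 18 patients, the listing of all adjustments shows every step, and the patient-level output already includes maximum dose, although its unit is not stated. The table shells are a separate document (SAP 11.1) and might break results down by level. No primary or secondary endpoint rests on this table.

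Most of that stands, and it limits the point to the specified summaries. It does not rescue the decrease category, which is named in the plan yet cannot register the decrease the protocol instructs. A correct listing does not repair the table.

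Three stronger readings may tempt a reader, and the documents do not support them:

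- *All step-downs are reported as increases.* This is true of 10 to 6 and 6 to 3. A 3 to 1 step is no change at constant weight.
- *Every reported decrease must be weight loss.* This needs mg to be recalculated on current weight, unrounded and without deviations. The documents state no such rule, and rounding or a deviation could also lower the mg amount.
- *About 3 to 5 patients will be misclassified by weight alone.* Applying 28.9% (13 of 45) to 10 to 18 patients gives 2.9 to 5.2. That is a ceiling: it assumes the earlier proportion carries over and that every such patient is miscounted.

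**Conclusion.** The point holds for the summary tables in SAP 6.5. With the lowest level as reference, no step-down appears as a level decrease: two of the three one-level step-downs are counted as increases (+500%, +200%) and the third as no change (0%) at constant weight. For 10 to 6 and 6 to 3, the classification as increases survives any plausible weight change.

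The further effect, that a patient held at 1 mg/kg is counted as changed, is conditional on mg being recalculated on current weight, or on rounding or a deviation. It should be stated as a possibility.

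The consequence is a descriptive exposure table that can mislead about de-escalation. The information is not lost, since the listing retains it. The correction is worth making because the table cannot do what it names and the repair is cheap. Nothing here bears on the dosing rule itself.

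**What to change.** In SAP 6.2.2 and 6.5, add or substitute a summary built on the prescribed mg/kg level:

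- Classify each infusion after the first as step-up, same or step-down against the level of the preceding infusion, and tabulate these by visit.
- Report per patient the maximum level reached, any step-up (yes/no) and any step-down (yes/no).
- If change from first dose is kept, express it as the mg/kg level at the visit, so that weight cannot create a change.

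Change both unit and reference, for the reason shown in step 5 of the working.

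**Cost.** One derived variable, a revised table shell and a short SAP edit. No new data are needed, because the dose level is already collected on the CRF.

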### **6.3. Subject Disposition**

The number of subjects will be calculated for all screened subjects. Subject will be considered screened after informed consent/assent is obtained.

Based on all screened subjects, the number and percentage of screen failures will be presented, as the main reason for screen failures will be tabulated. Screen failures will be listed.

Based on all screened subjects, the number and percentage of treated subjects who received the first dose of emapalumab will be presented.

Based on all treated subjects (subjects who received the first dose of emapalumab), the number and percentage of subjects who completed the treatment period prior to HSCT and those withdrawn from the treatment will be presented. The reason for withdrawal will be tabulated. Subjects withdrawn from the treatment period will also be listed.

Based on all subjects who completed the treatment period prior to HSCT, the number and percentage of subjects receiving HSCT and those who did not following the end of treatment will be presented. The reason for not receiving HSCT will also be tabulated.

Based on all subjects who completed the treatment period, the number and percentage of subjects who proceeded into the follow-up period and those who did not will be presented.

Based on all subjects who proceeded into the follow-up period, the number and percentage of subjects who completed the follow-up period and those who did not will be presented. The reason for withdrawal will also be tabulated. Subjects withdrawn from the follow-up period will also be listed.

Based on all screened subjects, the number and percentage of subjects included in the all treated analysis set will be calculated and summarized. A listing will be provided for subjects excluded from the analysis set with the reason of exclusion presented.

Based on all screened subjects excluding screen failures, important protocol deviation will be tabulated by protocol deviation category. Listings will be provided for all protocol deviations.

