6.5.1.3 Treatment period

Patients will be in the treating unit the day before the first administration of emapalumab SD-1.

During the treatment period, visits for infusion and safety /efficacy assessments will occur on SD0, and twice-a-week thereafter (not more than 4 days apart). After the patient's clinical condition is stabilized, decrease the dose to the previous level to maintain clinical response.

Given the unpredictable course of the disease, in case of reactivation (e.g. triggered by intercurrent infections), subsequent dose increases to 3 mg/kg (and up to 6 or 10 mg/kg, as appropriate) may need to be considered and will be guided by the same clinical and laboratory parameters described above and based on the Investigator's decision.

Treatment period will last until pre-conditioning for HSCT.

An end of treatment (EOT) visit has to be performed 3±1 days after last emapalumab infusion.

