6.5.1.4 Follow-up period

After treatment completion or treatment discontinuation (for any reason), patients will continue in the study for long-term follow-up until 1 year after either HSCT or last emapalumab infusion (if HSCT is not performed). This will represent the last visit in the study. If search for a donor is longer than 6 months, the follow-up period will be reduced, and the EOS will take place no later than 18 months after the first dose of emapalumab.

A patient who experiences HLH reactivation during the follow-up period, may be re-treated with emapalumab.

After the patient has completed the EOS visit, they should be treated and followed-up according to investigator judgment and local practice. No further investigational medicinal product will be provided.

In case of an ongoing SAE, the patient will continue to be monitored until resolution or until the outcome of the event is known and stable, beyond the defined study end as necessary.

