6.5.4.5 HSCT

Information about conditioning for HSCT and of the HSCT will be recorded in the eCRF. This information will be used to calculate the number and proportion of patients able to commence conditioning for HSCT

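### SAP 6.3 reports HSCT receipt and entry to follow-up only among treatment completers, so early stoppers whom the protocol keeps in follow-up have no place in either row

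*SAP*

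**What the plan says.** SAP 6.3 sets out disposition as a sequence of rows:

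- Out of all treated, "the number and percentage of subjects who completed the treatment period prior to HSCT and those withdrawn from the treatment will be presented". Reasons for withdrawal are tabulated and withdrawn subjects are listed.
- For transplant: "Based on all subjects who completed the treatment period prior to HSCT, the number and percentage of subjects receiving HSCT", together with those not transplanted and the reasons.
- For entry to follow-up: "Based on all subjects who completed the treatment period, the number and percentage of subjects who proceeded into the follow-up period".
- For the end of follow-up: "Based on all subjects who proceeded into the follow-up period, the number and percentage of subjects who completed the follow-up period". This row is not worded in terms of treatment completers.

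The visible SAP does not define completion of the treatment period.

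Protocol 6.5.1.4 says: "After treatment completion or treatment discontinuation (for any reason), patients will continue in the study for long-term follow-up". Protocol 6.3.3.1 and 11.1.3 also ask that patients who discontinue stay in follow-up. Protocol 6.5.1.3 places the end of treatment at transplant preparation: "Treatment period will last until pre-conditioning for HSCT". On the HSCT data, Protocol 6.5.4.5 says: "This information will be used to calculate the number and proportion of patients able to commence conditioning for HSCT". It names no denominator.

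**The concern.** The protocol follows every treated patient, whatever the reason emapalumab stopped. Its follow-up clock runs from HSCT or, without HSCT, from the last infusion, and this applies to discontinuers as well as completers. A transplant after early discontinuation is therefore foreseen. The two SAP rows do not allow for it: an early stopper who is followed or transplanted is in neither the numerator nor the denominator.

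Three things are at stake:

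- **Who is left out.** The primary endpoint is permanent discontinuation for emapalumab-related adverse events. On a plain reading those patients are not completers, so the table cannot show whether they were followed or transplanted.
- **Reconciliation.** Survival after HSCT (SAP section 3, Estimand 2.7, and 6.8.2) and post-HSCT outcome (SAP 6.12) cover treated patients who had HSCT, with no completion condition. The transplant count in disposition may not match theirs.
- **Comparability.** The study is meant to add to the profile from the global programme (Protocol 8.1). Protocol 4.1.1.3.2 reports transplant in NI-0501-04 as 70% of the treatment-experienced group and 65% of all treated. A completer-based percentage is a different quantity.

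**Working it through.** **1. The rule set against the protocol.** This step needs no assumed rates. Suppose, at the planned maximum of 18 treated (Protocol 6.1.1), 14 complete and 4 stop early, and all 18 are followed as the protocol asks. The follow-up entry row shows 14 of 14. The next row is based on everyone who entered follow-up, so its denominator is 18. Either the two rows disagree, or the four patients are dropped from both.

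**2. Direction of the HSCT percentage.** The documents give no expected transplant or completion rate for this trial, so there is no planned figure to reproduce. Let C be completers, W withdrawn, and c and w the numbers transplanted in each.

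- SAP row = c / C
- All-treated rate = (c + w) / (C + W)

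The SAP row is the higher one only when c/C exceeds w/W.

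**3. Illustration with NI-0501-04 (Protocol 4.1.1.3.2).** Inputs: 34 treated; 26 completed (26/34 = 76.5%, as stated); 65% of 34 transplanted, that is 22 (22/34 = 64.7%). Non-completers: 34 − 26 = 8. The documents do not say how the 22 divide between completers and non-completers, so the whole range is shown.

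| Non-completers transplanted (w) | Completer rate (22 − w)/26 | All-treated rate | Difference, points |
|---|---|---|---|
| 0 | 22/26 = 84.6% | 64.7% | +19.9 |
| 4 | 18/26 = 69.2% | 64.7% | +4.5 |
| 5 | 17/26 = 65.4% | 64.7% | +0.7 |
| 6 | 16/26 = 61.5% | 64.7% | −3.2 |
| 8 | 14/26 = 53.8% | 64.7% | −10.9 |

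The sign changes between 5 and 6 of the 8. Completion in that study meant at least 4 weeks of treatment plus short-term follow-up or continuation in NI-0501-05, so these counts are illustrative only.

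**4. Planned sample size.** Assumed: 2 of 10 or 4 of 18 stop early, and about 85% of completers are transplanted.

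| N | Completer rate | All-treated, no withdrawn patient transplanted | All-treated, every withdrawn patient transplanted |
|---|---|---|---|
| 10 | 7/8 = 87.5% | 7/10 = 70.0% | 9/10 = 90.0% |
| 18 | 12/14 = 85.7% | 12/18 = 66.7% | 16/18 = 88.9% |

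The exact 95% interval for 12/18 is 41.0% to 86.7%. If nobody withdraws, the two rates are equal.

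**The case against.** The strongest reply is that this is a labelled flow table, not an endpoint analysis. The row just above shows completers and withdrawals out of all treated, with reasons and a listing. HSCT receipt is not among the visible primary or secondary endpoints, and the study tests no hypothesis. All of that is correct and limits the weight of the point. It does not give a place to the patients whom Protocol 6.5.1.4 keeps in follow-up.

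A reader might go further and infer any of the following. The documents do not support them.

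- **That the SAP inflates the transplant rate.** Upward distortion is the likelier direction, because treatment runs to pre-conditioning and deaths on treatment would presumably count as withdrawals. But transplants in withdrawn patients are lost as well, and the sign can reverse. Nor does completion amount to transplant: Protocol 6.1 allows treatment completion where HSCT is not deemed indicated, and the SAP row has a category for completers who are not transplanted.
- **That early stoppers drop out of the trial's results.** The primary, safety, response, survival-to-conditioning and overall-survival analyses use all treated patients. Survival after HSCT takes any treated patient who was transplanted.
- **That follow-up percentages in general use completers.** Only entry to follow-up does.
- **That the plan contains no all-treated HSCT or conditioning proportion.** The exploratory endpoint sections (Protocol 5.2.2 and 8.3.5, SAP 6.9) are blank in the public documents, probably through redaction. They may hold one, and the SAP's default analysis set is all treated.

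**Conclusion.** The point holds for two rows of SAP 6.3. As worded, they leave out early stoppers whom the protocol keeps in follow-up, and the resulting counts may not reconcile with the post-transplant analyses or compare with the rates cited from NI-0501-04. That conflict rests on the text alone.

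The effect on the HSCT percentage is uncertain in size and sign. In the illustrations it is about 17 to 20 points upward when no non-completer is transplanted (84.6% against 64.7%; 87.5% against 70.0% at N = 10; 85.7% against 66.7% at N = 18). It is nil when nobody withdraws, and it reaches −10.9 points when all 8 non-completers in the NI-0501-04 example are transplanted. These figures rest on a transplant count derived from 65% of 34, on a different definition of completion, and on assumed withdrawal and transplant rates for this trial. It is a correction worth making, but it does not touch the primary analysis.

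**What to change.** In SAP 6.3, report HSCT received and entry to follow-up out of all treated patients, with separate rows for those who completed and those who were withdrawn from treatment. State who counts as having completed the treatment period, including patients who die on treatment and patients for whom HSCT is not indicated. The percentage among completers can stay as an additional, labelled row. Check that the transplant total equals the number in the survival-after-HSCT and post-HSCT outcome analyses.

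The cost is a change of denominator and a few rows in one table. HSCT is already recorded in the eCRF (Protocol 6.5.4.5), so no new data collection is evident. The drawback for the sponsor is that the headline HSCT percentage will probably look less favourable.
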